**Title: Effect of Progesterone on  
Testosterone concentrations and Breast  
development in Transwomen**

NCT04534881

Date: 9/13/2020

The number of individuals with gender incongruence who present to their physician for hormone therapy has increased manifold in the last decade(1). Testosterone therapy in transgender men (also known as female-to-male transgender or transmen) and estrogen therapy in transgender women (also known as male-to-female transgender or transwomen) respectively is the mainstay of hormone regimen. The proportion of individuals that are transwomen is slightly higher than transmen (60% vs 40%). Transwomen, who are genetically men, receive estradiol replacement with the aim of suppressing serum testosterone and achieving serum estradiol concentrations that mimic the serum concentrations of biological women. This leads to an increase in fat mass, breast growth and decreases in lean mass and masculine pattern hair. However, the results of these changes are often less than satisfactory and additional therapy is required.

Breast development is a major concern for transgender females. There is a great deal of variability among individuals, as evidenced during pubertal development (2). Transgender women do not achieve the same level of breast development as cisgender women do after puberty (3). Typically, transgender women plateau at Tanner stage III and half of the transgender women have a AAA cup size or less (4). In transwomen, breast development is generally maximal at 2 years after initiating hormones (5). However, a more recent study of 229 transgender women participating in the European Network for the Investigation of Gender Incongruence cohort found that breast development reached a plateau within the first 6 months of therapy. Half of the transgender women had a AAA cup size or less and only 10% were size A or more after a year of treatment (4). Not surprisingly, at least 60% of transgender women seek surgical breast augmentation (6).

There are transgender females who report an anecdotal improved breast development, mood, or sleep with the use of progestogens(7). Estrogen is important for stromal and early ductal and epithelial proliferation(2). By contrast, although progesterone in cell culture causes proliferation for a few days, it then transforms into its primary, maturational role that includes inhibition of the proliferative effects of E2 (7, 8). Progesterone appears to be relevant for acini/lobuli development and pseudolactational changes. Many women report a feeling of fullness in breasts and their transformation from a conical to more rounded shape (clinical experience of PI). Thus, progesterone may induce optimal breast maturation, if preceded by estradiol therapy in transwomen. However, observational studies with small number of patients do not support a major role for progesterone in enhancing breast size in transwomen (9). There have been no well-designed studies of the role of progestogens in feminizing hormone regimens, so the question is still open. As per Endocrine society transgender guidelines, “current evidence does not indicate that progestogens enhance breast development in transgender females, nor does evidence prove the absence of such an effect. This prevents us from drawing any firm conclusion at this moment and demonstrates the need for further research” (1).

Progesterone has a minor suppressive effect on GnRH production, and this would decrease endogenous testosterone production. In a chart review, transwomen using medroxyprogesterone (in combination with estradiol and spironolactone) had lower testosterone concentrations than those on estradiol and spironolactone alone (79 vs 215 ng/dl)(10). Progesterone also competes for the 5- $\alpha$  reductase enzyme that converts T into dihydrotestosterone (11). These effects would theoretically be desirable in the feminization of transwomen.

We plan to conduct a randomized, placebo controlled double blind study evaluating the effect of adding progesterone for 6 months to transwomen who are being treated with estradiol. We hypothesize

that progesterone will decrease serum testosterone concentrations as compared to placebo and increase breast size. We will also assess its role in mood, sleep, scalp hair and androgenic hair growth.

**Study endpoints: -**

- Serum testosterone concentrations (*primary endpoint*)
- Serum luteinizing hormone (LH) and follicle stimulating hormone (FSH) concentrations
- Breast size
- Hair growth
- Sleep quality
- Mood

**Study plan:** The study will be conducted by the division of Endocrinology at Saint Louis University. It is a randomized, placebo controlled double blind study. We expect to recruit patients from the PI's transgender clinic and from advertisements.

**Inclusion criteria**

1. Transwomen, currently on treatment with estradiol therapy for at least 6 months (as their standard of care gender affirming therapy)
2. Has achieved serum estradiol >100 pg/ml at least once, based on clinical labs in past.
3. Age 18-65 years

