2. HIV
3. Planning to go for breast enhancement or gender reassignment surgery in the next 6 months
4. Known history of peanut allergy (because the study drug contains peanut oil)
5. Active deep vein thrombosis, pulmonary embolism or history of these conditions
6. Active arterial thromboembolic disease or history of these conditions
7. Active cardiovascular disorders or history of these conditions (e.g. myocardial infarction, uncontrolled hypertension >150/90 mmHg)
8. Known, suspected, or history of breast cancer
9. Known liver dysfunction or disease
10. Known or history of gallbladder disease. This does not apply to subjects who have undergone cholecystectomy
11. Known or history of hypertriglyceridemia (>400 mg/dl)

**Screening visit:** Informed consent will be obtained. This visit may be conducted during the PI's clinic (if the study volunteer is PI's patient) or at Endocrinology clinical research space at Salus Center. Vital signs (blood pressure, heart rate and weight) will be measured and a general physical examination will be performed.

Subjects who qualify and consent to take part in the study will be assigned a number by a computerized random number generation program and will be randomized (1:1) to receive either progesterone or placebo. An unblinded pharmacist will prepare the study product. Study investigators, staff and the study participants will be blinded.

**Week 0 (baseline):** Subjects will come fasting to the Salus Center. Breast exam and testicular exam will be conducted. They will complete the study questionnaires. Blood sample will be taken for total testosterone, total estradiol, sex hormone binding globulin (SHBG), LH, FSH, complete blood count (CBC), comprehensive metabolic panel (CMP) and research labs. For subjects who are on intramuscular estradiol, this visit will be performed 3-4 days after their last injection. Subjects will be randomized to receive generic micronized progesterone 200 mg or placebo tablets, to be taken at bedtime daily. They will be given a 3-month supply of the study drug. Subjects will be asked to bring the pill bottles back with them at the next visit to assess compliance.

**Week 4:** Subjects will be called by the study coordinator to counsel on drug compliance and to ask for side-effects.

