- b) Symptom-Checklist-K-9 (SCL-K-9) to measure psychological distress level(20): This questionnaire has 9 questions and is meant to assess overall psychological distress. Responses are recorded on a 5 point Likert scale. The mean of all 9 questions is presented as the global severity index.

*Sleep quality:* We will use single-item sleep quality scale (SQS) to assess change in sleep quality during the study.

FG score calculator and study questionnaires are attached in the IRB application.

*Research labs:* 10 ml of blood will be obtained for research. Serum will be stored for future analysis based on study results. For example, if there is a decrease in FG score, we will check dihydrotestosterone levels.

**Side effects:** Progesterone may cause fluid retention, mood swings, breast tenderness, depression, transient dizziness and drowsiness, headache, abdominal pain or bloating, hot flashes in women. Long term use is associated with possibly increased risk of heart disease and stroke in women after menopause. Short term and long term risks in transwomen are not known.

If a significant or serious adverse event occurs, the subject will cease participation in the study. Discovery of two or more patients experiencing a significant or serious adverse event will lead to stopping of this study altogether.

**Statistical analysis:** The primary end-point of the study is change in total testosterone concentrations in transwomen after progesterone treatment at 24 weeks as compared to placebo. Transformations of the

data to meet statistical assumptions may be considered. *t*-test will be used for comparison. We estimate that testosterone concentrations will decrease by 20%. A sample size of 20 subjects per group (assuming a drop-out rate of 15%) will provide adequate power ( $\beta = 0.8$ ) to detect a significant difference ( $\alpha = 0.05$ ), provided the pooled standard deviation is not greater than the mean difference. Hence, we will recruit 40 transwomen in this study.

*Secondary end-points:* Change at weeks 12 and 24 in a) LH and FSH concentrations, b) breast size, breast hemi-circumference, areolar diameter, Tanner stage, feeling of fullness in breast, bra cup size, c) FG score, shaving frequency, scalp hair growth, scalp hair quality, d) global severity index scores on BUT-BIC and SCL-K-9 scales, e) SQS score.

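### Entry, randomisation and analysis all ignore baseline testosterone, so already-suppressed participants with intact testes may enter with little absolute room to show the primary effect

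*Combined protocol and SAP*

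**What the plan says.** The Statistical analysis paragraph (under Study Procedures) sets the endpoint: "The primary end-point of the study is change in total testosterone concentrations in transwomen after progesterone treatment at 24 weeks", compared with placebo by a t-test. The effect assumed is proportional and no starting level is given: "We estimate that testosterone concentrations will decrease by 20"%. The sample size is 20 per group, allowing for 15% drop-out, and holds "provided the pooled standard deviation is not greater than the mean difference". Transformation is mentioned as a possibility only.

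The Inclusion criteria have three items: "Transwomen, currently on treatment with estradiol therapy for at least 6 months", "Has achieved serum estradiol >100 pg/ml at least once, based on clinical labs in past", and an age range. None of the eleven exclusions refers to testosterone. The one that touches on surgery looks forward only: "Planning to go for breast enhancement or gender reassignment surgery in the next 6 months".

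The screening visit lists consent, vital signs and a physical examination. The study first measures testosterone at Week 0 ("Blood sample will be taken for total testosterone, total estradiol, sex hormone binding globulin (SHBG), LH, FSH"), the visit at which drug is dispensed, and no result is needed to proceed. Allocation is 1:1 with no stratification factor named.

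The introduction says that transwomen "receive estradiol replacement with the aim of suppressing serum testosterone". It also cites a chart review with testosterone of 79 ng/dl when medroxyprogesterone was added and 215 ng/dl on estradiol and spironolactone alone.

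**The concern.** The trial looks for a fall in testosterone in people already taking a treatment meant to lower it. The two estradiol conditions ask for exposure to that treatment and for evidence that estradiol once reached a given level. Nothing asks what happened to testosterone. Someone with testes in place whose testosterone is already low is eligible, and in that person a 20% fall amounts to a few ng/dl.

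If such participants are a material share of 40, the mean difference in ng/dl shrinks faster than the spread. A null result would then be hard to read: progesterone may not lower testosterone, or too few participants had testosterone left to lower. Nothing in the randomisation or the prespecified analysis would separate the two. Prior gonadectomy is a different matter and is not part of this point.

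**Working it through.** **Inputs.** From Statistical analysis: 20 per group, 15% drop-out, α = 0.05 (two-sided assumed, as the plan does not say), power 0.80 (written there as β), SD no greater than the mean difference (so standardised effect d of at least 1), and a 20% fall. From the introduction: 215 ng/dl without a progestogen. Assumptions that the documents do not supply: the suppressed share f, a suppressed level of 30 ng/dl, and an SD of change of 6 ng/dl in the suppressed.

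**1. The plan's own figure.** For a two-sample t-test with d = 1 and n per arm, the noncentrality is d√(n/2). With n = 17 it is √8.5 = 2.92 and power is 0.807; with n = 16 power is 0.781. Then 17/(1 − 0.15) = 20 per group. The stated sample size reproduces, with almost nothing to spare.

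**2. Room to fall.** 0.20 × 215 = 43 ng/dl; 0.20 × 30 = 6 ng/dl.

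**3. Suppressed participants show no change and almost no variation (ng/dl scale).** Give the others a mean difference of 1 and an SD of 1.

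- Mean difference overall: 1 − f.
- Placebo variance: 1 − f.
- Progesterone variance: (1 − f) + f(1 − f) = (1 − f)(1 + f).
- Average variance: (1 − f)(1 + f/2), so d = √[(1 − f)/(1 + f/2)].

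| f | d | Power, 17 per arm |
|---|---|---|
| 0 | 1.00 | 0.81 |
| 0.2 | 0.85 | 0.67 |
| 0.3 | 0.78 | 0.60 |
| 0.5 | 0.63 | 0.43 |

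Simulation of 40,000 trials agrees (0.673, 0.605 and 0.428).

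**4. Suppressed participants keep the 20% fall (ng/dl scale).** The others fall 43 with SD 43; the suppressed fall 6 with SD 6.

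- f = 0.25: mean difference 0.75 × 43 + 0.25 × 6 = 33.75. Placebo variance 0.75 × 43² + 0.25 × 6² = 1395.75. Progesterone variance adds 0.25 × 0.75 × (43 − 6)² = 256.69, giving 1652.44. Average SD 39.0, d = 0.86, power 0.69.
- f = 0.5: mean difference 24.5, variances 942.5 and 1284.75, average SD 33.4, d = 0.73, power about 0.55 (0.56 by simulation).

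**5. Same fall on a log scale.** A 20% fall is ln 0.8 = −0.223 at any baseline. If the SD of log change is also 0.223 in everyone, d = 1 whatever f is, and power stays at 0.81. The documents do not give that SD.

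**6. Comparison within the not-suppressed stratum.** With d = 1 and 17(1 − f) per arm (13.6, 11.9 and 8.5 at f = 0.2, 0.3 and 0.5), power is 0.71, 0.64 and 0.49.

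**The case against.** The strongest reply is that the premise is undocumented. The only testosterone level for people on estradiol without a progestogen is 215 ng/dl, and a 20% fall from there is 43 ng/dl. Suppression is stated as an aim of therapy, and the introduction adds that results often fall short. The estradiol criterion asks for one past value, not for current suppression. This stands: a reader might infer that the entry rule selects suppressed participants, and the documents do not show that. But one summary level from another cohort does not show that few are suppressed either.

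Second, the plan's effect is a percentage and transformation is allowed, so a constant proportional fall need lose no power. This also stands, but only in part. Transformation is merely possible under the plan, and it does not help if the proportional fall is itself smaller in the suppressed.

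Third, the power statement is conditional. A reader might infer that the stated 80% is wrong. The arithmetic is right, and the SD condition can be read as applying to the whole enrolled sample and allows d above 1. With d = 1.25 in the others, the model in step 3 gives 84% at f = 0.2 and 76% at f = 0.3.

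Fourth, harsher figures (59%, 47% and 27% at f = 0.2, 0.3 and 0.5) follow if the suppressed vary in ng/dl as much as everyone else while showing no effect. That does not fit people whose values barely move, so these figures should not be used.

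Finally, broad entry is a legitimate choice. The question concerns transwomen treated with estradiol, and breast development is in the title. A testosterone threshold would narrow the population for every other endpoint, and the documents support no particular cut-off.

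**Conclusion.** The gap is real, but its size is unknown. No entry criterion, stratification factor or analysis step takes account of baseline testosterone, so already-suppressed participants with intact testes can be randomised and analysed without distinction. If the other participants just meet the plan's d = 1 condition, the cost on the ng/dl scale ranges from about 12 percentage points of power (81% to 69%, a quarter suppressed but keeping a 20% fall) to about 38 points (81% to 43%, half suppressed with no change). On a log scale with a constant 20% fall and equal spread it is essentially nil. All of this rests on assumed values of f and of the suppressed level and spread.

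The documents do not support concluding that the trial is underpowered, that most participants will be suppressed, or that eligibility must change. They do support a cheap improvement that makes a null result interpretable.

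**What to change.** Keep entry open and make three changes before enrolment.

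1. Stratify randomisation by the most recent clinical total testosterone, suppressed or not, at a cut-off that the sponsor fixes in advance. The week 0 result is not required before drug is dispensed, so the clinic value is the practical one.
2. Prespecify the testosterone comparison in the not-suppressed stratum as a supportive analysis.
3. Make the primary analysis log testosterone at week 24, adjusted for the week 0 value already collected, and report the ratio of progesterone to placebo. On that scale the planned effect corresponds to a ratio of 0.80.

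The cost is one stratification factor in a 40-person trial. The estradiol criterion already sends staff to past clinic results, but a recent testosterone may be missing for some people recruited by advertisement, so the plan should say how they are stratified. The supportive analysis has limited power of its own (about 71%, 64% and 49% at f = 0.2, 0.3 and 0.5); its value lies in interpretation. The third change needs no new measurement.

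A testosterone threshold at entry remains an option for the sponsor to weigh against a narrower population for the breast and other endpoints. It is not a required correction.

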**Exclusion Criteria**

1. Treatment with progesterone in the last 2 months

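### Exclusion 1 names only progesterone, so users of another progestogen can be randomised and none is barred from starting one during the 24 weeks, which dilutes the treatment contrast

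*Combined protocol and SAP*

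**What the plan says.** The first item under Exclusion Criteria reads, in full, "Treatment with progesterone in the last 2 months". No other inclusion or exclusion item mentions a progestogen. The background therapy required at entry is estradiol: participants must be "currently on treatment with estradiol therapy for at least 6 months".

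The opening background text does not treat progesterone as the only relevant drug. It uses the class term when it says "There have been no well-designed studies of the role of progestogens in feminizing hormone regimens", and it cites a chart review in which users of medroxyprogesterone, with estradiol and spironolactone, had testosterone of 79 ng/dl, against 215 ng/dl without it. For the breast it proposes that "progesterone may induce optimal breast maturation, if preceded by estradiol therapy in transwomen".

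Participants "will be randomized (1:1) to receive either progesterone or placebo" (Screening visit). No stratification factor is given. The Statistical analysis paragraph defines the primary endpoint as "change in total testosterone concentrations in transwomen after progesterone treatment at 24 weeks as compared to placebo", to be compared by t-test, and names no adjustment for progestogen use. The visit descriptions contain no rule on concomitant medication and no medication history. The week 4 call covers compliance and side-effects only.

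**The concern.** The trial asks what progesterone adds to estradiol. That needs participants who are not already receiving, and do not later receive, a related drug acting on the same outcome. The exclusion secures this for recent progesterone only. A current medroxyprogesterone user meets the criteria as written and may continue it in either arm. The criterion also looks back only, whereas exclusion 3 looks forward 6 months for planned surgery. Nothing therefore discourages a participant from obtaining a progestogen elsewhere after week 0.

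Such users are plausible. The background says that some transgender women report benefit from progestogens, and recruitment is from a transgender clinic and advertisements. At stake is the reading of a null result: with little spare power, a modest share of participants in whom the study drug has less to add could hide a real effect on testosterone.

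**Working it through.** **Inputs from the Statistical analysis paragraph.** 20 per group, 15% drop-out, alpha 0.05, power 0.8 (printed there as beta), an expected fall of 20%, and a pooled SD no larger than the mean difference, so a standardised effect d of at least 1.0. Sidedness is not stated; two-sided is assumed.

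**Step 1: reproduce the plan's figure.** A two-sample t-test (non-central t) with d = 1.0 and power 0.80 needs 16.7, so 17 completers per arm. 17 / (1 − 0.15) = 20 per group, as stated. Power with 17 per arm is 0.807, so there is almost no margin.

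**Step 2: how stable users enter the contrast.** Let f be the share of stable users in each arm and k the fraction of the full effect that study progesterone still has in them.

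- Placebo arm: a stable user carries the other drug's effect in the baseline and is expected to change by about zero, like any other placebo participant.
- Active arm: non-users change by Δ and users by kΔ, so the mean change is (1 − f)Δ + fkΔ.
- Effective standardised effect: d = 1 − f(1 − k), with the SD held at its planned value.

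**Step 3: range for k.** The documents do not give k. Two assumptions are used:

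- k = 0: study progesterone adds nothing in users.
- k = 0.37: the same 20% fall applies, but from the lower level. 0.20 × 215 = 43 ng/dl and 0.20 × 79 = 15.8 ng/dl; 15.8 / 43 = 0.37.

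**Step 4: power with 17 completers per arm.**

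| Assumed f | d, k = 0 | Power | d, k = 0.37 | Power |
|---|---|---|---|---|
| 0% | 1.00 | 0.81 | 1.00 | 0.81 |
| 10% | 0.90 | 0.72 | 0.94 | 0.75 |
| 20% | 0.80 | 0.62 | 0.87 | 0.69 |

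For scale, 20% of 34 completers is about 7 people. The SD is not adjusted in the table. In the k = 0 case, mixing two kinds of response in the active arm adds f(1 − f)Δ² to that arm's variance, which lowers power slightly further, to 0.70 at 10% and 0.59 at 20%.

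**Step 5: what the table leaves out.** A placebo participant who starts a progestogen after week 0 can show a real fall in testosterone during the study. That reduces the contrast from the other side and is not in these figures.

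**The case against.** The strongest reply is that this is only loose wording. The background moves straight from progesterone's effect on GnRH to the medroxyprogesterone data, as though the terms were interchangeable, and site staff may read the criterion as covering the class. That is possible, but the criterion does not say so, and it would not cover the 24 weeks in any case.

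A second reply is that the shares are invented and that k = 0 is a worst case. Both points stand, which is why the result is a range conditional on an assumed share.

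Three stronger readings are tempting and should be resisted.

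- A reader might infer that a progestogen user on placebo already has the effect under test and so shrinks the difference. For a change-from-baseline endpoint this is not so if use is stable; it applies only to someone who starts during the study.
- A reader might infer that the comparison is biased. Allocation is randomised 1:1 and blinded, so users at entry fall in both arms on average. The harm is dilution, added variance and possible chance imbalance in 40 people, not type I error inflation.
- A reader might infer that past progesterone users enter with breast maturation already complete and must be excluded. The documents are silent on whether any such change persists. The background presents the effect as a possibility and notes that small observational studies do not support a major one. The point bears mainly on secondary endpoints, no size can be put on it, and excluding past users would cost recruitment.

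**Conclusion.** The gap is real: followed literally, the eligibility rule admits current users of other progestogens, and nothing governs non-study progestogens from week 0 to week 24. The consequence is a loss of power. At an assumed 10% share of stable users, power falls from 0.81 to between 0.72 and 0.75; at 20%, to between 0.62 and 0.69. These figures rest on a standardised effect of exactly 1.0, 17 completers per arm, a two-sided test, an unchanged SD, equal shares in the two arms, and k between 0 and 0.37. The actual share is unknown and may be small.

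The gap between 79 and 215 ng/dl is 63% (1 − 79/215), but it comes from a non-randomised review of a different drug. It shows why the class matters to the primary endpoint and does not measure a causal effect. The plan should be corrected on this point; the point does not invalidate the design.

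**What to change.** 1. Reword exclusion 1 to cover treatment with progesterone or any other progestogen, naming medroxyprogesterone as an example. The length of washout is a clinical decision for the sponsor.
2. State that non-study progestogens are not to be used from week 0 to week 24, ask about them at each contact, and record any use.
3. Record prior progestogen exposure at screening, before randomisation, and prespecify a sensitivity analysis of the secondary breast endpoints by prior use.

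The cost is one reworded criterion, one added rule and a few history questions, with perhaps a few otherwise eligible patients lost or delayed. The sample size stays at 20 per group. By the same formula and drop-out inflation, leaving the gap open and restoring 80% power by recruitment would need 23 to 25 per group at an assumed 10% share (19 or 21 completers, divided by 0.85) and 26 to 31 at 20% (22 or 26 completers, divided by 0.85).
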